 - Unable to read and speak English since consent will only be available in English

[figure not shown]
- d) Study Endpoints
 - Primary endpoints: Participation in the study will end after the third visit.
 - Primary safety endpoints: none
 - Secondary safety endpoints:
 - Adverse reaction to the laser treatment such as blister, ulceration, and scarring.
 - Adverse reaction to the topical steroid such as atrophy, telangiectasias or striae.
 - Intolerance to pain of laser procedure.

- e) Study Timelines
 - Each participant will be in the study for a maximum of 8 weeks. Participants will receive 2 laser treatments. The laser treatments will be spaced 4 weeks apart between visit 1 and visit 2. Finally, 4 weeks after visit 2, the participants will be followed up during visit 3.

 - The duration expected for all study participants to be recruited is estimated to be 28 weeks.

 - The study will end when the last participant has completed the 2 laser treatments and follow up. The goal is to conclude the data collection by October 31, 2018 and complete primary analysis by December 31, 2018.

- f) Procedures involved in the Human Research.
- This study will be a randomized prospective study. All study lesions will receive topical treatment. One lesion will only receive topical treatment to serve as a control, and up to 2 others will also receive laser treatment in addition to the topical treatment.
 - Standard of care treatment will be a topical corticosteroid as follows:
 - Discoid lupus lesions: Betamethasone dipropionate augmented 0.05% cream twice a day as needed
 - Non-discoid cutaneous lupus lesions: Triamcinolone acetonide 0.1% cream twice a day as needed
 - Laser treatment will be randomized based upon the participant Fitzpatrick Skin Type as follows:
 - Fitzpatrick Skin Types I – III:
 - § Treatment lesion will be treated with 532nm laser or 1064nm laser
 - § 50:50 randomization for laser used (determined by coin flip)
 - § If the participants have an additional lesion then this will be treated with the laser not used for the treatment lesion
 - Fitzpatrick Skin Types IV - VI
 - § Treatment lesion will only be treated with the 1064nm laser. This is because the 532 nm wavelength is absorbed easily by melanin and thus can cause skin pigmentation abnormalities when used with darker skin participants.
 - Laser treatment system details and parameters:

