g) Data and specimen management

There will be no specimen collection, and thus there will be no management of physical specimens.

If a participant withdraws from the study, the reason for the withdrawal will be noted but data collected up to that point will be used.

All data will be collected on the survey documents (see attached documents “Survey” and “Independent Observer Survey”). These survey documents will be stored in regulatory binder in a locked drawer in locked room at UCF Health. This will only be accessible only to the principal investigator and co-principal investigators. These survey documents will then be used to transfer the data to the REDCap database, afterwards they will be disposed of in HIPAA-compliant shred bin.

Photographs of study lesions will be stored directly in the EHR.

The data will be analyzed for significant differences with aid of a statistician. A significance level of 0.05 will be used for statistical hypothesis testing. The results of the data analysis will be graphed for each parameter.

h) Provisions to monitor the data for the safety of participants

The principal investigator and statistician will periodically review cumulative CLASI scores and adverse effect data every 10 patients.

If the change in the active CLASI score for the treatment lesion is 3 points higher than the change in the active CLASI score for control lesions with $p < 0.05$ then the study will be suspended immediately.

If participants have ulceration or scarring attributable to the laser treatment as an adverse effect with $p < 0.05$ then the study will be suspended immediately.

i) Withdrawal of participants

Participants will be withdrawn from the research without their consent if they become intolerant to the laser treatments and/or the investigators determine that they are too nervous, anxious to continue.

Participants may terminate their participation in the research study at any time by informing a member of the research team. If the participant declines any further laser treatments he or she may still participate in the study with follow up assessments being completed.

If participants miss study Visit 2, the researchers will attempt to reach the participant to reschedule. If the participant is unable to reschedule within 2 weeks of the missed appointment then the participant will forego the 2nd treatment and attempted to be scheduled for Visit 3.

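### Participants judged intolerant to laser leave the research, while those who decline laser or miss the second treatment stay under assessment, so later outcomes are lost selectively by laser tolerability

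*Combined protocol and SAP*

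**What the plan says.** Section 7 i) (Withdrawal of participants) describes three ways in which laser treatment can end early.

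- Intolerance or anxiety: "Participants will be withdrawn from the research without their consent if they become intolerant to the laser treatments". The rule has a second trigger, which is an investigator's judgement that nerves or anxiety stand in the way. What the participant leaves is the research, not only the laser.
- Participant's choice: "If the participant declines any further laser treatments he or she may still participate in the study with follow up assessments being completed".
- Missed Visit 2 that cannot be rebooked in time: "the participant will forego the 2nd treatment and attempted to be scheduled for Visit 3".

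Section 7 g) (Data and specimen management) says of any withdrawal that "the reason for the withdrawal will be noted but data collected up to that point will be used". No passage provides for assessments after a withdrawal. Section 7 d) lists "Intolerance to pain of laser procedure" among the secondary safety endpoints. Section 7 e) sets the last assessment: "Finally, 4 weeks after visit 2, the participants will be followed up during visit 3", which is Week 8. The timeline in section 7 f) lists the Visit 2 lesion assessment before the second treatment. The documents define no analysis population and no method for missing data.

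**The concern.** In all three cases the participant stops receiving laser, but only the first ends outcome collection. A participant who finds the procedure too painful could fall under the first rule or the second, depending on whether the investigators or the participant act first.

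Three things are at stake. First, the Week 8 laser-versus-control comparison would describe people who tolerated laser, not everyone who started it. Second, adverse effects that take time to show, such as scarring or pigment change, could go unseen after withdrawal, both in the final counts and in the cumulative safety review of section 7 h). This would follow from reaching an event that the plan itself lists as a safety endpoint. Third, the plan hypothesises that 532 nm is more effective than 1064 nm. If the two wavelengths differ in tolerability, withdrawals would fall unevenly and could distort that comparison.

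The control lesion leaves with the participant. The problem is therefore selection of participants, not missing data in one arm only.

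**Working it through.** **1. Which assessments are lost.** Inputs: the visit schedule in sections 7 e) and 7 f), and the rules in 7 g) and 7 i).

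| Event | Stays under assessment? | Lesion assessments kept | Lesion assessments lost |
|---|---|---|---|
| Withdrawn at treatment 1 (Week 0) | No | Baseline | Weeks 4 and 8 |
| Withdrawn at treatment 2 (Week 4) | No | Baseline, Week 4 | Week 8 |
| Declines further laser | May stay | All, if the participant stays | None, if the participant stays |
| Misses Visit 2, not rebooked | Visit 3 to be attempted | Baseline, Week 8 if attended | Week 4 |

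A participant withdrawn at treatment 1 contributes no change score for any lesion.

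**2. Size of a possible bias.** The plan gives no intolerance rate, dropout allowance or figure for this loss, so there is no figure of its own to reproduce. The one input from the documents is the planned 25 participants (section 7 a).

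Let k be the number withdrawn, C the mean laser-minus-control change in completers, and W the mean that the withdrawn would have shown. Then:

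- mean over all participants = [(25 − k)C + kW]/25
- completers-only estimate = C
- bias = C − [(25 − k)C + kW]/25 = (k/25)(C − W)

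If k = 0 or C = W, the bias is zero. For an assumed 1-point gap between C and W on the limited active CLASI (range 0 to 5):

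| k (assumed) | k/25 | Bias, gap 0 | Bias, gap 1 point |
|---|---|---|---|
| 1 | 0.04 | 0 | 0.04 |
| 2 | 0.08 | 0 | 0.08 |
| 3 | 0.12 | 0 | 0.12 |
| 5 | 0.20 | 0 | 0.20 |

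The bias scales with the gap and takes its sign. If the withdrawn would have done better than completers, laser would be understated.

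**3. Chance that it arises at all.** With an assumed intolerance rate p and 25 participants, the probability of at least one is 1 − (1 − p)^25. This is 22% for p = 1%, 72% for p = 5% and 93% for p = 10%.

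**4. Precision.** With the standard deviation unchanged, losing 5 of 25 pairs widens the standard error by a factor √(25/20) = 1.118, about 12%. This is secondary to the selection.

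**The case against.** The strongest reply is that the loss is narrow and its effect on efficacy unproven. Much of that stands.

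- A reader might infer that outcomes are lost in the people whose lesions do worst on laser. The documents do not support this. The listed endpoint concerns pain of the procedure, and the second trigger is anxiety. Nothing links either to a worse CLASI change, and section 8 lists pain and scarring as separate risks with very different frequencies.
- A reader might also infer that the laser effect will be overstated by some definite percentage. That would need an intolerance rate, an outcome in the withdrawn and a completers-only analysis. The plan states none of these, and its rule on using data up to withdrawal leaves room for an analysis that uses Week 4 scores.
- Data before withdrawal are kept, the reason is recorded, and pain is scored after each treatment. The intolerance event itself is therefore captured; what can be missed is later events.
- Many participants who cannot bear laser may decline it themselves and so remain under assessment.
- The explicit statement that data collection stops appears only in the rule for a missed Visit 3. For intolerance, the end of assessment is a reading of withdrawal from the research, though the natural one, because the next paragraph grants continued assessment only to those who decline.

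The conflict between the rules is left untouched by this. Followed as written, section 7 i) makes later data collection depend on laser tolerability.

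**Conclusion.** The point holds as a conflict between stated rules. Participants withdrawn for intolerance or anxiety lose Weeks 4 and 8, or Week 8 only, for every study lesion, while others who stop laser can be assessed to the end. The consequences are a Week 8 comparison confined to laser-tolerant participants, possible under-recording of late adverse effects, and possible distortion of the wavelength comparison if tolerability differs.

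The direction and size of any efficacy bias are unknown. The range of 0.04 to 0.20 points rests on an assumed 1 to 5 withdrawals, an assumed 1-point gap and a completers-only analysis; with no withdrawals or no gap it is zero. The text does not establish worse lesion outcomes in intolerant participants. The change is still worth making, because the loss is avoidable and the plan already applies the better principle to those who decline.

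**What to change.** Reconcile the rules in section 7 i) by separating stopping laser from leaving the study. State that any participant whose laser treatment stops, for whatever reason and on whoever's decision, is asked to complete the scheduled Visit 2 and Visit 3 assessments of all study lesions, unless that participant withdraws consent for follow-up. Add that these assessments enter the analysis under the treatment assigned to each lesion at Visit 1; otherwise they could be collected and then set aside. When laser is stopped remains the investigators' decision, and nothing here bears on it.

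The cost is about two sentences and no new visits, since both are already in the schedule. The downside is that a few participants, including some withdrawn for anxiety, would be asked to attend assessment visits that they would otherwise have skipped. They remain free to refuse.

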In addition participants will rate the cosmetic results on a visual analog scale (VAS).

A score of 0 will represent a cosmetically fully unsatisfactory result and 10 will represent cosmetically excellent result.

- Adverse Effects:

Pain: After each treatment pain will be recorded on VAS. A score of 0 will represent absence of pain and 10 will represent maximal pain.

Other adverse effects that will be monitored for:

- Hyperpigmentation
 - Hypopigmentation
 - Crusting
 - Vesiculation
 - Scarring
- Risk Management:
Participants will be directly observed for any adverse effects during treatment. The chances of a research related injury are extremely rare. However treatment for research related minor injuries will be made available at no cost by [name] if possible. For injuries that cannot be treated by [name] the participant will be referred elsewhere. Costs associated with this treatment may be billed to the participant's insurance company. Costs not covered by participant's insurance company will be the participant's responsibility.

Participants will not be misled in anyway about procedures/activities being performed

Research will be conducted during [name] clinical time.

The duration of research should take approximately 12 months. The research study will begin recruitment directly after IRB approval in hopes of being finished by December of 2018.

No audio or video recordings will be used in this study. However photographs will be taken of the lesions for assessment purposes. Though the photos will not contain any identifiers, participants are potentially identifiable from the photos and thus they will be stored in the HIPAA-compliant electronic health record (EHR) of UCF Health.

A study survey document (see attached "Survey" and "Independent Observer Survey") will be used to record the following:

- Age
- Gender
- Pregnancy Status
- Fitzpatrick Skin Type
- Past Medical History
- Medications
- Allergies
- Lesion locations
- Lesion type
- Lesion treatment
- Limited CLASI
- Patient cosmetic assessment

- Whether patient would recommend treatment
- Pain and adverse effect assessment

Note: the above information will be collected from the medical records and during the study visits.

Medical records in the HIPAA-compliant EHR at UCF Health will be used to obtain the following data:

- Age
- Gender
- Past Medical History
- Medications
- Medication Allergies
- Social History
- Photographs
- Laboratory Results

Student/school records are not to be used.

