If participants miss study Visit 3, the researchers will attempt to reach the participant to reschedule. If the participant is unable to reschedule within 6 weeks of the missed appointment then the participant will be withdrawn from the study. Further data collection will not be continued.

8) Risks to participants

Laser treatment association risks^{15,16,19}:

Risks: >50%

- Pain/Discomfort – Additionally sharp burning/stinging pain can occasionally be felt.

Risks: <10%

- Redness/Swelling/Bruising – Short term redness (erythema) or swelling (edema) of the treated area is common and may occur. There also may be some bruising.
- Skin Color Changes – During the healing process, there is a possibility that the treated area may become either lighter (hypopigmentation) or darker (hyperpigmentation) in color compared to the surrounding skin. This is usually temporary, but, on a rare occasion, it may be permanent.
- Itching/Burning/Dry skin – Treatment may result in itching, burning, and/or dry skin during the recovery period.
- Red Rash/Bumps – Red rash/bumps may appear after treatment. This resolves with time.
- Acne flare-up or cold sore – this may occur after treatment.

Risks: <1%

- Wounds – Treatment can result in burning, blistering, scabbing, or bleeding of the treated areas.
- Infection – Infection is a possibility whenever the skin surface is disrupted, although proper self-wound care should prevent this.
- Scarring – Scarring is a rare occurrence, but it is a possibility when/if the skin surface is disrupted. To minimize the chances of scarring, it is important that participants follow all post-treatment instructions provided by the research staff. (see attached pre- and post-treatment instructions)

Other risks:

- Sun Exposure / Tanning Beds/ Artificial Tanning - May increase risk of side effects and adverse events and must be avoided.
- Eye Exposure – Protective eyewear (shields or goggles) will be provided to the participant during the treatment. Failure to wear protective eyewear during the entire treatment may cause severe and permanent eye damage.
- Lack of improvement (procedure may not work) or exacerbation of cutaneous lupus.

There is unknown risk to the an embryo or fetus should the participant be pregnant as none of the clinical trials with the laser were performed on pregnant women.

There are no risks to an embryo or fetus should the participant become pregnant.

There is no risk to non-participants.

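### Data collection stops, with no exception for safety, when Visit 3 cannot be rescheduled within 6 weeks, so delayed harm from the laser may go unrecorded

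*Combined protocol and SAP*

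**What the plan says.** Section 7) e) sets laser treatments at Visits 1 and 2, four weeks apart, and then: "Finally, 4 weeks after visit 2, the participants will be followed up during visit 3". In the timeline of section 7) f), Visit 3 consists of the final lesion assessment. Its limited damage CLASI scores dyspigmentation and scarring. No other contact is scheduled after the second treatment.

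Section 7) i) covers a missed Visit 3. Its first step is: "If participants miss study Visit 3, the researchers will attempt to reach the participant to reschedule". If the visit cannot be held within 6 weeks of the missed appointment, "then the participant will be withdrawn from the study. Further data collection will not be continued".

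Four other provisions bear on this:

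- Section 7) d) lists as a safety endpoint: "Adverse reaction to the laser treatment such as blister, ulceration, and scarring". Section 7) h) makes ulceration and scarring attributable to the laser grounds for suspending the study, with cumulative data reviewed every 10 patients.
- Section 7) g) says of a participant who withdraws that "the reason for the withdrawal will be noted but data collected up to that point will be used".
- Section 7) f) has pain scored after each treatment and participants observed while treated. It names medical records, alongside the visits, as a source for the survey items, which include adverse effects. It also states: "Medical records in the HIPAA-compliant EHR at UCF Health will be used to obtain the following data", with photographs on the list that follows.
- Section 7) i) lets a participant who declines more laser stay for follow-up, and sends one who misses Visit 2 on to Visit 3.

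**The concern.** Failing to attend a visit is not withdrawal of consent, yet here it ends all data collection on a participant who has been treated. The harms at stake are mostly delayed. Section 8) places colour change in the healing period, and a scar cannot be seen on the day of treatment. For the second laser, Visit 3 is the one planned look at such effects. For someone who also missed Visit 2 and went without the second laser, it is the one planned look after the first.

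The rule is also stricter than its neighbours in section 7) i), which keep people in follow-up after they stop laser or miss Visit 2. With 25 participants and reviews every 10, one unseen scar or ulcer is a noticeable part of the safety evidence. Recovering it later would be hard, because section 11) has the list linking names to study numbers destroyed at study completion.

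**Working it through.** **Timing.** On the nominal schedule the second laser is at week 4 and Visit 3 at week 8. A Visit 3 held up to 6 weeks late falls at week 8 + 6 = 14, which is 14 − 4 = 10 weeks after the second laser. Section 7) e) caps participation at 8 weeks, so the two provisions conflict and must be reconciled.

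**What is captured after the second laser if Visit 3 never happens.**

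| Source | Under the plan |
|---|---|
| Pain score and observation on the day | Recorded (7 f) and kept (7 g) |
| Adverse effects charted before withdrawal | Usable (7 f, 7 g), but nobody is told to look |
| Adverse effects mentioned when staff call to rearrange | Not excluded, but nobody is told to ask |
| Anything arising after withdrawal | Not collected (7 i) |

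**Inputs for size.** N = 25 (section 7 a). Scarring is listed in section 8) under risks below 1% and colour change under risks below 10%; I use 1% and 10% as upper values. The plan has no loss figure to reproduce, so I assume 0 to 5 of 25 lost at Visit 3.

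**Formulas.** With n participants seen and event rate p, the expected events are n × p, the chance of seeing at least one is 1 − (1 − p)^n, and the one-sided 95% upper bound after zero events is 1 − 0.05^(1/n).

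| Lost | Seen (n) | Zero-event bound | Expected events, 1% / 10% | Chance of at least one, 1% / 10% |
|---|---|---|---|---|
| 0 | 25 | 11.3% | 0.25 / 2.5 | 22.2% / 92.8% |
| 1 | 24 | 11.7% | 0.24 / 2.4 | 21.4% / 92.0% |
| 3 | 22 | 12.7% | 0.22 / 2.2 | 19.8% / 90.2% |
| 5 | 20 | 13.9% | 0.20 / 2.0 | 18.2% / 87.8% |

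**Direction of bias.** Take a true rate of 10%, so that 2.5 of 25 are harmed and 22.5 are not.

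- 30% of harmed and 10% of unharmed lost: 2.5 × 0.7 = 1.75 events among 1.75 + 22.5 × 0.9 = 22.0 seen, a rate of 8.0%.
- 10% lost in both: 2.25 events among 2.25 + 20.25 = 22.5 seen, a rate of 10%.
- 5% of harmed and 20% of unharmed lost: 2.375 events among 2.375 + 18 = 20.375 seen, a rate of 11.7%.

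The event count falls in every case. The rate among those seen can fall, stay the same or rise.

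**The case against.** The strongest reply is that the plan already loses little. One missed appointment does not end follow-up, since there is a rescheduling attempt and a 6-week window. The stop applies only from withdrawal, so adverse effects reported or charted before then may be used. Pain and observation are recorded on the day of treatment. Participants have the investigator's contact details, and section 12) offers care for minor research injuries where possible, so a harmed participant has a way back to the clinic. Contact is attempted and not assured, so added questions yield nothing from people who cannot be reached. The loss rate is assumed, and the bound barely moves.

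Most of this stands, and it rules out several stronger readings that a reader might infer. The documents do not support saying that missing Visit 3 in itself ends data collection, that the rule forbids using the rescheduling contact or the record, or that there is no safety information at all after the second laser. Nor do they show that harm is under-counted as a rate, because people whose lesions have cleared may also stay away. A single unseen scar (1/25 = 4%) would not contradict the stated risk below 1% either: at a true 1%, at least one scar in 25 has a 22.2% chance.

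What the reply does not remove is the gap itself. Nobody is instructed to ask about or look up delayed harm before withdrawal, and anything arising after it is excluded, although consent has not been withdrawn.

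**Conclusion.** The point holds as an omission in safety follow-up. Treated participants whose Visit 3 cannot be held within 6 weeks leave the study with no planned capture of delayed ulceration, scarring or pigment change, which are effects the plan itself monitors. The number of recorded events can only fall as a result. Whether the observed rate is too low or too high depends on who is lost, which is unknown.

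The numerical effect is modest: for an assumed 1 to 5 lost of 25, the zero-event bound moves from 11.3% to between 11.7% and 13.9%. The effect on the suspension review cannot be calculated, because section 7) h) gives a p-value threshold but names no test. The case for change rests on the value of a single safety event in a study of 25 and on the low cost of capturing it.

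**What to change.** In section 7) i), replace "Further data collection will not be continued" with text to this effect:

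> Unless the participant withdraws consent, staff who reach the participant to reschedule Visit 3 will ask about and record the listed laser and steroid adverse effects, by lesion. Adverse effects and lesion photographs charted in the UCF Health EHR up to a fixed date will be recorded with their date, as the consent and HIPAA authorization allow.

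State the fixed date, for example the end of the 6-week window or study close-out. It must come before the linking list is destroyed. Include these data in the safety counts, marked as participant-reported or record-based, and keep them out of the week-8 efficacy analysis. Report how many participants have no safety assessment after their last treatment. Separately, reconcile the 8-week maximum in section 7) e) with the 6-week window in section 7) i).

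The cost is a short amendment, a few questions at a contact already to be attempted, a record look-up, and a check of the consent and HIPAA wording, which may need revision. The data will be irregular and partly self-reported. The look-up may cover a longer period than attenders have, which is why dates are needed. Participants recruited from outside the clinic may have no later record there, and those who cannot be reached may still contribute nothing.

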 - The Excel V laser system manufactured by Cutera (Brisbane, CA) will be used to administer all laser treatments. This laser has the capability of emitting both 532nm and 1064nm wavelengths.
 - Treatments with the 532nm wavelength will utilize parameters in the following ranges:
 - § Spot size: 1-12mm
 - § Fluence: 5-12 J/cm²
 - § Pulse Duration: 3-15ms
 - § Temperature: 5-10°C
 - Treatments with the 1064nm wavelength will utilize parameters in the following ranges:
 - § Spot size: 1-12mm
 - § Fluence: 10-60 J/cm²
 - § Pulse Duration: 10-60ms
 - § Temperature: 5-10°C
 - Note: If the lesions are ill-defined such as those of ACLE and SCLE then a lesion will be defined as a 2cm² within the involved area.

- Timeline:

Pre-Week 0: Screening Visit

- Screening: participant will be screened for inclusion and exclusion criteria, including urine pregnancy test if necessary.

Week 0: Visit 1

- Baseline lesion assessment, lesion selection, randomization and treatment 1 will occur.

Week 4: Visit 2

- Follow up lesion assessment
- Treatment 2

Week 8: Visit 3

- Final lesion assessment

- Lesion assessment:

Limited CLASI:

The classification of cutaneous lupus will be recorded for each participant.

A “limited” CLASI scoring system will be used, subdivided into an “active” and “damage” components.

The limited active CLASI for a lesion will include the following:

- Erythema (ranging from 0 = absent to 3 = dark red/purple)
- Scale/Hypertrophy (ranging from 0 = absent to 2 = verrucous/ hypertrophic)
- The addition of these scores result in a total limited active CLASI score of the studied lesion, ranging from 0 to 5.

The limited damage CLASI for a lesion will include the following:

- Dyspigmentation (0 = absent or 1 = present)
- Scarring/Atrophy/Panniculitis (ranging from 0 = absent to 2 = severely atrophic scarring or panniculitis).
- The addition of these scores result in a maximum damage score of 3.

The total limited CLASI reflects the sum of both active and damage CLASI, resulting in a score ranging from 0 to 8.

Photographs will be taken of all study lesions during every assessment.

All participants will be evaluated by [name] at baseline and at subsequent visits.

All participants will be evaluated via photograph by [name] at baseline and subsequent visits. [name] will be blinded to the treatment type so as to be an independent observer. He will utilize the “Independent Observer Survey” to document his assessments.

Visual Satisfaction of Appearance:

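### Section 8 calls fetal risk unknown if a participant is pregnant, then denies any risk if she becomes pregnant; the two conflict for conception between the two laser treatments

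*Combined protocol and SAP*

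**What the plan says.** Section 8, at the end of the laser risks, has two adjacent sentences on pregnancy. The first reads "There is unknown risk to the an embryo or fetus should the participant be pregnant" and gives as its reason that "none of the clinical trials with the laser were performed on pregnant women". The second reads "There are no risks to an embryo or fetus should the participant become pregnant", with no time limit, reason or citation.

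Other parts of the protocol bear on the same point:

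- Section 7(c) makes pregnancy an exclusion criterion, and Section 16 says pregnant participants will not be used.
- The timeline in Section 7(f) puts the only pregnancy test at screening: "participant will be screened for inclusion and exclusion criteria, including urine pregnancy test if necessary". Its entry for visit 2 at week 4 has two items, "Follow up lesion assessment" and treatment 2.
- Pregnancy status is on the list of survey items in Section 7(f), with the note that "the above information will be collected from the medical records and during the study visits".
- Section 7(i) gives the grounds for withdrawal by the investigators: "Participants will be withdrawn from the research without their consent if they become intolerant to the laser treatments", or if they are judged too nervous or anxious to go on. Pregnancy is not among them.
- On a missed visit 2, Section 7(i) says: "If the participant is unable to reschedule within 2 weeks of the missed appointment then the participant will forego the 2nd treatment".

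**The concern.** The second sentence is a positive safety assurance, and it follows directly on a statement that the risk is not known. Laser is given twice, four weeks apart, so a participant can become pregnant during the study and still be due for laser. For her, the reason the protocol gives for calling the risk unknown applies in full, and nothing in the document supports the assurance.

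The error is in the unsafe direction. Section 6 says everyone assisting in the study receives the protocol, so this is the text they would consult if a participant reported a pregnancy before visit 2. Section 4 says that women aged 20 to 50 are the group most often affected by cutaneous lupus, so the case is not remote for this population. What is at stake is participant safety and accurate risk information, not the analysis.

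**Working it through.** The plan states no figure on this point, so there is none to reproduce. The check sets the two sentences against the visit schedule.

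**Inputs**

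- Laser treatments: 2, at week 0 and week 4 (Sections 7(e) and 7(f)).
- Allowed delay of treatment 2: 2 weeks after the missed appointment (Section 7(i)). I take this to mean that the rescheduled visit takes place within 2 weeks.
- Final visit: week 8, with no laser (Section 7(f)).
- Pregnancy tests listed: one, at screening, if necessary (Section 7(f)).

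**Exposure window**

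- Interval between treatments, on schedule: 4 − 0 = 4 weeks.
- Interval with the longest allowed delay: (4 + 2) − 0 = 6 weeks.
- Laser sessions still to come after a conception in that interval: 2 − 1 = 1.
- Pregnancy tests scheduled in that interval: 0, because the only one listed precedes treatment 1.
- Study time after the last laser, on schedule: 8 − 4 = 4 weeks.

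**The two sentences by time of conception**

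| Conception | Pregnant at a laser session? | First sentence | Second sentence | Conflict |
|---|---|---|---|---|
| Before treatment 1 | Yes | Unknown risk | Not clearly applicable | No; also excluded at entry |
| Between treatments 1 and 2 | Yes, at treatment 2 | Unknown risk | No risks | Yes |
| After treatment 2 | No | Not applicable if tied to laser exposure | No risks | No |

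Only the middle row conflicts. That participant has become pregnant and is pregnant when treated.

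**Do other provisions settle the middle row?** The exclusion criterion works at entry. The statement in Section 16 can be read as barring laser in a known pregnancy, but it sets no means of finding one. The survey item could find one, but the protocol body names no visit for it and attaches no action to the answer. The withdrawal grounds are silent on pregnancy, and no contraception requirement is stated. No check or stopping rule is therefore in place before treatment 2.

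**The case against.** The strongest reply is that the difference in verb is deliberate: the first sentence is about pregnancy at the time of exposure, the second about pregnancy arising later. On that reading a woman who conceives before treatment 2 is pregnant when treated, the first sentence governs, and the reader has just seen it. Add the exclusion criterion, Section 16, and the collection of pregnancy status during visits, and it is unlikely that a known pregnancy would be lasered on the strength of one sentence. All treatments are given by one clinician, so the decision does not rest with staff at large. The survey form and the pre- and post-treatment instructions are attachments not available here, and the form may be organised by visit. Finally, confirming status from a survey item could miss an early, unrecognised pregnancy.

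Much of this is fair. The sentences can be reconciled for conception after the last laser, and treatment of a recognised pregnancy is improbable. But the limit has to be supplied by the reader, and a risk section should not depend on that when the unlimited reading is the unsafe one. The other provisions reduce the chance of harm; they do not correct the assurance or put a check before treatment 2. The comment on the survey item shows that it is a minimum safeguard: repeating the urine test would be stronger. The unseen attachments limit what can be said about the survey's layout, not about Section 8.

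**Conclusion.** The concern holds. Section 8 makes an unqualified assurance that contradicts the sentence before it for any conception between the two laser treatments: a window of 4 weeks, or about 6 if visit 2 is rescheduled, with 1 of the 2 laser sessions then falling in pregnancy and no scheduled test in between. It does not extend to the final 4 weeks, when no laser is given.

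Three limits apply. The 6-week figure rests on the stated reading of the rescheduling rule. The number of the 25 participants who could be affected cannot be derived, because the sex and age mix is not given. What participants themselves are told depends on the consent form, which was not available. The point should be corrected for safety and disclosure; it leaves the endpoints, power and error rates as they are.

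**What to change.** 1. In Section 8, delete the second sentence and extend the first: the risk to an embryo or fetus is unknown if the participant is pregnant or becomes pregnant before her last laser treatment. Alternatively, keep a no-risk statement only for conception after the last treatment, and give its basis.
2. In the visit 2 entry of Section 7(f), add that pregnancy status is confirmed before treatment 2, using the item already on the survey, and that laser is withheld if she is pregnant.
3. Check the consent form and bring it into line if it carries the same wording.

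The cost is one sentence deleted, one extended, one status check before treatment 2, and a look at the consent form. No visit is added and the analysis does not change. Withholding laser need not lose follow-up: Section 7(i) already lets a participant who declines further laser stay for assessments.
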